## 8.2 Number of Participants to be Enrolled

The sample size for the study will be at least 177 participants randomized per group (at least 354 total randomized). The hypothesis is that vascular status as assessed by PWV will be improved by statin therapy. Specifically, there will be a significant group (drug vs. placebo) by time interaction effect on mean PWV in a repeated measures analysis appropriately controlled for participant and clinical site specific random effects.

Although reports of longitudinal measures or clinical trials using PWV in youth are nonexistent, our investigators reported data from lean and obese youth age 10-24 years who were age, race, and sex matched using the same SphygmoCor device proposed for this study. In 241 lean participants (BMI <85th%ile), carotid-femoral PWV was 5.4 (0.7) compared with 6.3(1.1) in 234 non-diabetic obese participants (BMI ≥95th%ile). Obese youth had PWV 14% greater than lean youth. Two statin trials used PWV measured by the same SphygmoCor system to provide baseline and end of study vascular data for adults (average age 50s). In 20 adults with rheumatoid arthritis treated with simvastatin for 6 weeks, PWV dropped from 9.6 (2.3) at baseline to 8.9 (2.1), a 7.4% decrease from baseline. In 35 hypercholesterolemic adults treated with rosuvastatin plus low-fat diet for 4 weeks, PWV dropped from 9.5 (1.9) to 7.8 (1.5), a decrease of 18% from baseline.

Sample size was computed under several scenarios based on different values for the group by time interaction effect size in the 2 treatment groups (statin and placebo/no drug) assuming baseline PWV 6.3±1.1 m/sec and, based on unpublished data from [name] et al. collected 5-years apart on 268 obese youth, a correlation within participants for repeated measures over time of 0.5 [observed value from [name] et al. was 0.68]; alpha 2-sided = 0.05, power (1-beta) = 0.85, equal n for each group, equal assignment to treatment group at each clinical center and no stratification factors beyond treatment group, as follows:

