### 8. STATISTICS

## 8.1 Statistical Analysis Plan

The primary analytic approach for all trial outcomes will be intention-to-treat (ITT). Several secondary analytic approaches will also be examined as outlined below and discussed in detail in a separate Statistical Analysis Plan (SAP).

- Non-intention-to-treat (NITT): Participants will be classified according to treatment
  actually received. NITT analyses, while potentially more powerful due to less dilution of
  treatment effect compared to an ITT analysis, are subject to bias because the inherent
  balance and lack of bias provided by randomization in measured and unmeasured
  patient characteristics of the two treatment groups is not preserved.
- Non-intention-to-treat by duration of pitavastatin use: If a substantial fraction of
  participants either cross-over from placebo to pitavastatin or are prescribed open-label
  pitavastatin or other statin therapy by their treating physicians, analysis will be
  conducted with 'time-under-statin' as a continuous or stratifying (categorical) predictor of
  change in the outcomes.
- Exclusion of ineligible participants: Secondary analyses will be conducted after exclusion of participants who were later found to have been ineligible at the time of randomization.
- Covariate-adjusted analysis: adjustment for baseline (pre-randomization) factors known to be associated with a particular outcome can increase the efficiency of the treatment effect comparison. Such factors will be identified from the literature and used as covariates in the trial outcome analyses.

Descriptive statistics will be used to determine the distribution of values for all variables, and variables requiring transformation to meet analytic assumptions will be appropriately transformed. Data analysis plans will be keyed to the specific aims as follows, and incorporate appropriate methodology as described below.

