### **Assumptions:**

- 1. Baseline pulse wave velocity (PWV) is normally distributed with a mean of 6.3 m/sec and a standard deviation of 1.1 m/sec.
- 2. In addition to the baseline PWV measurement, PWV will be measured at after six months, 12 months, and 24 months.
- 3. Any change in PWV over the two-year duration of the study is conservatively assumed to be linear in time (i.e., 25% of the change will be observed at the six month visit, 50% of the change will be observed at the 12 month visit, and 100% of the change will be observed at the 24 month visit).
- 4. The following 3 hypotheses (scenarios) are considered:
  - a. In Scenario 1, the PWV will remain unchanged in the control group over the twoyear duration of the study and will decrease 8% in the statin group over the same 2-year period.
  - b. In Scenario 2, the PWV will decrease 5% in the control group over the two-year duration of the study and will decrease 11% in the statin group over the same 2-year period.

- c. In Scenario 3, the PWV will remain unchanged in the control group over the twoyear duration of the study and will decrease 5% in the statin group over the same 2-year period.
- 5. The within-participant correlation between any pair of PWV measurements is assumed to be 0.5.
- 6. The sample size is adjusted by 20% to account for participant dropout.
- 7. The effect of crossover has not been incorporated into these sample size calculations.

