## **Sample Size Calculations:**

The mean slope (change) over two years of follow-up can be calculated as:

$$\mu_{s} = \overline{PWV}_{24} - \overline{PWV}_{0}$$

Where  $\overline{PWV_0}$  and  $\overline{PWV_{24}}$  are the mean PWV at baseline and 24 months, respectively.

The variance of the slope over two years of follow-up can be calculated as:

$$\sigma_s^2 = \frac{\sigma^2}{SS_t} (1 - \rho)$$

Where  $\sigma$  is the standard deviation of PWV (assumed to be constant over time for the purposes of these calculations),  $\rho$  is the within-participant correlation between pairs of PWV measurements,  $SS_t = \sum (t_i - \bar{t})^2$ , and  $t = \{0, 0.25, 0.5, 1\}$  (since the assumed changes were given over two years of observation, it is easier to use this formulation for time).

After calculating the mean slopes for both the control and statin groups and the standard deviation of the slope, the Inequalities Tests for Two Means (Two-Sample t-Test) module of PASS was used to calculate the required sample size assuming a two-sided type 1 error rate of 5% and 85% power. The sample sizes required under each of the three scenarios are listed as follows:

Scenario	$\Delta_c$	$\Delta_t$	$Slope_c$	$Slope_t$	$\sigma_s$	N/group
1	0%	8%	0	-0.504	1.052	100
2	5%	11%	-0.315	-0.693	1.052	177
3	0%	5%	0	-0.315	1.052	253

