A secondary hypothesis is that the carotid bulb (site of earliest disease) CIMT of the statin group will be lower than in the placebo group at study end. In adults, progression on placebo is about 0.01 to 0.02 mm/year compared to improvement of 0.01 to 0.02 mm/year with rosuvastatin, which results in a mean difference of 0.04 mm over 2 years. Adult studies using a lifestyle intervention and small studies of children have showed no effect of lifestyle on CIMT. The only pediatric study (mean age 13 years) using a statin was conducted in children with FH. Over the 2 year study, the investigators observed progression of IMT of +0.005 (SD 0.044) in control and regression -0.01 (SD 0.048) in pravastatin treated youth. These are underestimates since the investigators averaged all 3 carotid segment measures, and the common carotid is known to demonstrate a slower progression than the bulb and internal carotid measures. Since a longitudinal study of 84 non-diabetic obese youth in Cincinnati had internal CIMT progression of 0.015 mm for 2 years (with SD 0.1) and the current study will use a potent statin, pitavastatin, a better estimate of effect size would be progression of 0.01 mm in the placebo group and regression of 0.02 mm over 2 years in the statin group, which yields a difference of 0.03 mm. Also, newer auto edge detection software as will be used in this study (as compared to manual trace used above) has smaller SD of 0.06 to 0.07.293 Using the higher SD of 0.07, and assuming a correlation of repeated measures over time = 0.3, at a two-sided alpha of 0.05, to achieve power of 0.85 to detect a significant group X time interaction in CIMT would require 177 randomized participants per group (including 20% drop-out).

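### The primary PWV slope test, as framed and sized, does not use the equality of baseline means that randomization provides; a common baseline mean would raise power from about 85% to about 93% on the plan's own inputs at the same sample size

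*Protocol*

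**What the plan says.** Section 8.1.1 gives the primary hypothesis as a between-arm difference in PWV slope over two years. Its analysis sentence says only that changes will be compared across all visits, and it leaves the detailed plan to the SAP, which was not available for this review.

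Section 8.2 is more specific. It expects that "there will be a significant group (drug vs. placebo) by time interaction effect on mean PWV in a repeated measures analysis", with random effects for participant and clinical site. No baseline term or constraint is named. The sizing that follows introduces a formula with the words "The variance of the slope over two years of follow-up can be calculated as": sigma²(1 − rho)/SS_t, with time scaled as 0, 0.25, 0.5 and 1. A two-sample t-test on slopes is then run in PASS, "assuming a two-sided type 1 error rate of 5% and 85% power".

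Section 8.1 recognises that "adjustment for baseline (pre-randomization) factors known to be associated with a particular outcome can increase the efficiency of the treatment effect comparison", but it lists covariate adjustment with the secondary analyses.

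**The concern.** PWV is measured at month 0 and allocation is randomized 1:1, so any difference between the arms' baseline means is chance. A slope contrast that gives each arm its own baseline mean estimates that chance difference and carries its noise into the treatment effect.

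Two things follow. The trial gives up power that its baseline visit has already paid for. The estimate also moves with chance baseline imbalance: an arm that happens to start high tends to show a steeper fall. Section 8.4 already plans for the SD assumption being wrong, so extra margin that needs no new participants is worth having.

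**Working it through.** **Inputs (Section 8.2).** Baseline PWV is "normally distributed with a mean of 6.3 m/sec and a standard deviation of 1.1 m/sec". On correlation: "The within-participant correlation between any pair of PWV measurements is assumed to be 0.5"; the value observed in the unpublished data is given as 0.68. Visits are at t = 0, 0.25, 0.5, 1. The Scenario 2 slopes are −0.315 and −0.693, a difference of 0.378 m/s. Dropout is 20%, so 177 × 0.8 = 141.6; 141 completers per arm are used below.

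**1. Reproducing the plan.**
- Mean t = 0.4375 and SS_t = 0.546875.
- Slope SD = √(1.1² × 0.5 / 0.546875) = 1.052, as stated.
- A two-sample t-test at 85% power and two-sided 0.05 needs 141 per group, and 141/0.8 rounds up to 177, as stated.
- Scenarios 1 and 3 also reproduce (80 gives 100; 202 gives 253).

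**2. What that variance implies.** Take V = sigma²[(1 − rho)I + rho J], A = 1′V⁻¹1, B = 1′V⁻¹t and C = t′V⁻¹t. At rho = 0.5, A = 1.3223, B = 0.5785 and C = 1.1570.
- Separate baseline mean in each arm: variance of the slope difference = 2/[n(C − B²/A)]. Here C − B²/A = 0.9039, and 1/√0.9039 = 1.052, the plan's slope SD. The sizing formula is therefore the separate-baseline case.
- Common baseline mean: variance = 2/(nC).
- Ratio of the two = 0.9039/1.1570 = 0.781, a reduction of 21.9%.

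**3. Power at 141 per arm**, as Φ(difference/SE − 1.96):

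| Case | Separate baselines | Common baseline |
|---|---|---|
| rho 0.5, 0.378 m/s | SE 0.1253, 85.5% | SE 0.1107, 92.7% |
| rho 0.5, 0.315 m/s (Scenario 3) | 71.0% | 81.2% |
| rho 0.68, 0.378 m/s | SE 0.1002, 96.5% | SE 0.0936, 98.1% |

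Put another way, at rho 0.5 the common-baseline test would reach 85% power with 109 completers per arm.

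**4. Sensitivity to chance imbalance.** The slope's weight on the baseline visit is (0 − 0.4375)/0.546875 = −0.8. A baseline difference d is expected to shift the slope difference by −0.8(1 − rho)d. One standard error of the baseline difference is 1.1 × √(2/141) = 0.131 m/s. The shift is then 0.8 × 0.5 × 0.131 = 0.052 m/s, about 14% of 0.378.

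**5. Alternatives that use baseline as a covariate** (rho 0.5, 0.378 m/s, 141 per arm).
- Post-baseline values, no separate group term: SE 0.1107, 92.7%, the same as the common-baseline model.
- Baseline-adjusted difference at month 24: SE = √(2 × 1.21 × 0.75/141) = 0.1135, 91.5%.
- Post-baseline values with a free group term, testing group-by-time: only months 6, 12 and 24 inform the slope (SS_t = 0.2917). SE = √(2 × 0.605/(141 × 0.2917)) = 0.1715, about 60%.

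**6. If true slopes vary between participants.** The documents give no figure for this. Assuming a slope SD of 0.3 to 0.7 m/s over two years, power goes from 82.7% to 90.1% at the low end and from 71.0% to 77.9% at the high end. The gain stays near 7 points.

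**The case against.** The strongest reply is that the protocol never says the primary model has a separate baseline mean in each arm. A common-baseline model is also a group-by-time interaction in a repeated-measures analysis, and the SAP may already specify one. The formula belongs to the sizing, and a conservative sizing variance does not bind the analysis. This stands: separate baselines are inferred from the formula and from the secondary place given to adjustment. It limits the claim to how the test is framed and sized. It does not remove the case for stating the model.

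A second reply is that 0.5 was chosen below the observed 0.68, where the gain is only 1.6 points. That also stands, and the two results belong side by side. But 0.5 is the value on which the trial was sized.

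Three stronger readings are tempting, and the documents do not support them:
- A reader might infer that baseline PWV is discarded. It is not: it is the time-0 point of every slope. What goes unused is the expected equality of the arm means.
- A reader might infer that the sample size or the test is wrong. The sample size reproduces exactly, and an unconstrained slope comparison is valid.
- A reader might put a similar figure on CIMT, where the plan works "assuming a correlation of repeated measures over time = 0.3". With SD 0.07 and a difference of 0.03 mm, the PWV formula gives 88.9% power at 141 completers per arm, but the protocol reports 85% for 177 randomized. The formula does not reproduce the plan's CIMT calculation, so no CIMT gain is claimed here.

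**Conclusion.** The point holds as an efficiency gain that needs no new data or participants. It is not an error in the plan. On the protocol's own assumptions (SD 1.1, equal correlation 0.5 between all visits, linear change, 0.378 m/s, 141 completers per arm), a common baseline mean lowers the variance by about 22% and raises power from about 85% to about 93%. At a correlation of 0.68 the trial is well powered either way and little is gained. The benefit is therefore largest where the design is most exposed: a lower correlation or a smaller effect than hoped.

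The hypothesis tested and the nominal 5% level are unchanged. A simulation of 4000 trials with estimated variance components gave type I error of 5.0% with a common baseline and 5.4% with separate ones, and power of 93.3% and 85.4%. If the SAP already constrains or adjusts for baseline, what remains is to align Sections 8.1, 8.1.1 and 8.2 with it.

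**What to change.** In Sections 8.1.1 and 8.2, and in the SAP if it does not already say so, state that the primary repeated-measures model takes baseline PWV as an outcome with a mean common to both arms. The model has time and group-by-time terms and no group main effect at time 0. Keep the participant and center random effects and keep N at 177 per group. Use the same model for CIMT.

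If baseline PWV is to be a covariate instead, choose one of two forms. Either omit the group main effect, so that the treatment effect is zero at time 0, or make the baseline-adjusted month-24 difference the test (about 91.5% power). Do not test group-by-time in a post-baseline model that also has a free group term; that drops power to about 60%.

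The cost is a sentence or two in each document and one fewer model term, to be fixed before any unblinded look at the data.

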### **Assumptions:**

- 1. Baseline pulse wave velocity (PWV) is normally distributed with a mean of 6.3 m/sec and a standard deviation of 1.1 m/sec.
- 2. In addition to the baseline PWV measurement, PWV will be measured at after six months, 12 months, and 24 months.
- 3. Any change in PWV over the two-year duration of the study is conservatively assumed to be linear in time (i.e., 25% of the change will be observed at the six month visit, 50% of the change will be observed at the 12 month visit, and 100% of the change will be observed at the 24 month visit).
- 4. The following 3 hypotheses (scenarios) are considered:
  - a. In Scenario 1, the PWV will remain unchanged in the control group over the twoyear duration of the study and will decrease 8% in the statin group over the same 2-year period.
  - b. In Scenario 2, the PWV will decrease 5% in the control group over the two-year duration of the study and will decrease 11% in the statin group over the same 2-year period.

- c. In Scenario 3, the PWV will remain unchanged in the control group over the twoyear duration of the study and will decrease 5% in the statin group over the same 2-year period.
- 5. The within-participant correlation between any pair of PWV measurements is assumed to be 0.5.
- 6. The sample size is adjusted by 20% to account for participant dropout.
- 7. The effect of crossover has not been incorporated into these sample size calculations.

## **Sample Size Calculations:**

The mean slope (change) over two years of follow-up can be calculated as:

$$\mu_{s} = \overline{PWV}_{24} - \overline{PWV}_{0}$$

Where  $\overline{PWV_0}$  and  $\overline{PWV_{24}}$  are the mean PWV at baseline and 24 months, respectively.

The variance of the slope over two years of follow-up can be calculated as:

$$\sigma_s^2 = \frac{\sigma^2}{SS_t} (1 - \rho)$$

Where  $\sigma$  is the standard deviation of PWV (assumed to be constant over time for the purposes of these calculations),  $\rho$  is the within-participant correlation between pairs of PWV measurements,  $SS_t = \sum (t_i - \bar{t})^2$ , and  $t = \{0, 0.25, 0.5, 1\}$  (since the assumed changes were given over two years of observation, it is easier to use this formulation for time).

After calculating the mean slopes for both the control and statin groups and the standard deviation of the slope, the Inequalities Tests for Two Means (Two-Sample t-Test) module of PASS was used to calculate the required sample size assuming a two-sided type 1 error rate of 5% and 85% power. The sample sizes required under each of the three scenarios are listed as follows:

Scenario	$\Delta_c$	$\Delta_t$	$Slope_c$	$Slope_t$	$\sigma_s$	N/group
1	0%	8%	0	-0.504	1.052	100
2	5%	11%	-0.315	-0.693	1.052	177
3	0%	5%	0	-0.315	1.052	253

Therefore, the conservative estimate of 11% decrease in PWV with statin treatment and 5% decrease in PWV with placebo at 2 years including 20% drop-out results in the need to randomize at least 177 participants per group for a total of at least 354 to detect an absolute difference of 6% in change in PWV between statin and placebo arms at an alpha of 0.05 and power of 0.85 for the group by time interaction. Assuming a crossover from placebo to openlabel statin of no more than 5% by the end of the trial (from feasibility data from 9 sites, 22 of 454 potentially eligible participants had at least one LDL-C >160 mg/dL during follow-up and not continuously), this will result in a marginal dilution of the treatment effect such that these sample size estimates ultimately apply to an absolute difference of approximately 5.94% in change in PWV between treatment and placebo. It should be noted that the sample size of 177 randomized participants per group is conservative since recent data from Cincinnati suggest that non-diabetic obese participants on no drug therapy will have progression of PWV around 0.05 m/sec/year or 0.1 m/sec over the 2-year grant (presented at American Society of Hypertension meeting May 2013). Therefore, it is likely that the placebo group will show no improvement in PWV or more likely, progression (worsening; increase) in PWV.

A secondary hypothesis is that the carotid bulb (site of earliest disease) CIMT of the statin group will be lower than in the placebo group at study end. In adults, progression on placebo is about 0.01 to 0.02 mm/year compared to improvement of 0.01 to 0.02 mm/year with rosuvastatin, which results in a mean difference of 0.04 mm over 2 years. Adult studies using a lifestyle intervention and small studies of children have showed no effect of lifestyle on CIMT. The only pediatric study (mean age 13 years) using a statin was conducted in children with FH. Over the 2 year study, the investigators observed progression of IMT of +0.005 (SD 0.044) in control and regression -0.01 (SD 0.048) in pravastatin treated youth. These are underestimates since the investigators averaged all 3 carotid segment measures, and the common carotid is known to demonstrate a slower progression than the bulb and internal carotid measures. Since a longitudinal study of 84 non-diabetic obese youth in Cincinnati had internal CIMT progression of 0.015 mm for 2 years (with SD 0.1) and the current study will use a potent statin, pitavastatin, a better estimate of effect size would be progression of 0.01 mm in the placebo group and regression of 0.02 mm over 2 years in the statin group, which yields a difference of 0.03 mm. Also, newer auto edge detection software as will be used in this study (as compared to manual trace used above) has smaller SD of 0.06 to 0.07.293 Using the higher SD of 0.07, and assuming a correlation of repeated measures over time = 0.3, at a two-sided alpha of 0.05, to achieve power of 0.85 to detect a significant group X time interaction in CIMT would require 177 randomized participants per group (including 20% drop-out).

## 8.3 Level of Significance

The type I error probability for the trial treatment comparisons will be 0.05 (two-sided). No adjustment will be made to account for comparing the treatment groups with respect to more than one outcome variable. However, the report will note the number of comparisons made, and the possibility that when many outcomes are analyzed, it is not unexpected that one or more might have a statistically significant treatment difference by chance.

## 8.4 Interim Analyses and Stopping Rules for Termination of the Study

#### Interim Evaluation of Sample Size Assumptions

Unforeseen inaccuracies in design assumptions, in particular having to do with the estimated variance (SD), could lead to decreases in the trial's statistical power to detect treatment effects. Accordingly, a blinded analysis will be conducted, during enrollment to estimate the SD of the estimated slope in both treatment arms. This analysis will be conducted within the intention-to-treat framework under which the primary analysis of the primary endpoint will be conducted (**Section 8.1**).

To allow time for corrective action if necessary, after approximately 30% of participants have data collected from their 6-month visit, an interim analysis will be performed (estimated to occur between 12 and 15 months after study initiation depending on enrollment ramp-up). The DSMB will review and approve/modify proposed corrective actions (see SAP for details on proposed actions).

